## **10.2 Study-Drug Accountability**

The PI is responsible for ensuring that a current record of inventory/drug accountability (NGM282 and rosuvastatin) is maintained. Inventory records must be readily available for inspection by the study monitor and are open to inspection by regulatory authorities at any time. Each shipment of drug supply for the study will contain a shipping manifest to assist the PI in maintaining current and accurate inventory records.

Upon receipt of the investigational drug, the designated site personnel will visually inspect the shipment, verify the number and condition of study drug received, and confirm receipt of study drug.

At the completion of the study and after all drug accountability has been performed by the site CRA, all unused study-drug supplies will be returned to the Sponsor (or designee) or disposed of by the clinic, per the Sponsor's (or designee's) written instructions.

## **10.3 Study-Drug Storage**

NGM282 syringes are to be stored at the clinical site in the provided packaging and refrigerated at 2°C–8°C (36°F–46°F) in a secure, controlled-access location protected from light. At the subject's home, NGM282 syringes are to be stored in the provided packaging protected from light and refrigerated. All drug excursions should be reported immediately to Sponsor to confirm NGM 282 stability.

Rosuvastatin calcium tablets should be stored at room temperature, at 68°F–77°F (20°C– 25°C) and in a dry place. Excursions are permitted to 59°F–86°F (15°C– 30°C) Please refer to package insert USP Controlled Room Temperature. (Appendix D)

Subjects will be instructed to take care in keeping both study drugs out of the reach of children and other family members.

## **10.4 Dose Preparation and Administration**

### **10.4.1 NGM282**

Subjects will be instructed to dose with NGM282 at relatively the same time each day. For visit days in the clinic, subjects will not dose at home.

Study-drug syringes should be brought to room temperature (~15-20 minutes) prior to use and administered as a SC injection in the abdomen. On Day 1, subjects will be trained on SC self-injecting. During the on-treatment visits, SC self-injecting will occur in the clinic under observation by clinic staff. Re-training will be provided as required. Written dose preparation and administration instructions will be provided to subjects. Subjects will be required to complete a daily study-drug administration diary.

[figure not shown]
#### **10.4.2 Rosuvastatin**

[figure not shown]
Only subjects in the open-label single-blind and placebo-controlled 24-week histology cohorts who meet specific on-treatment criteria will be instructed to dose rosuvastatin based on the LDL-C levels at Weeks 2, 4, and 8 or at the discretion of the medical monitor.

Additionally, subjects in the placebo-controlled 24-week histology cohort who have not achieved an adequate response or are unable to tolerate statin therapy may be considered for second-line lipid-lowering therapy with ezetimibe at the discretion of the medical monitor.

Ezetimibe is formulated as 10mg tablets and can be administered with or without food at the same time as rosuvastatin. This must be approved by the Sponsor's Medical Monitor prior to dosing with ezetimibe and will be prescribed by the Investigator. The specific treatment algorithms will be based on whether subjects are statin naïve ([Section 10.4.2.1](#)) versus statin experienced ([Section 10.4.2.2](#)) at Baseline as outlined in the following figures for subjects in both the open-label single-blind and placebo-controlled 24-week histology cohorts:

**10.4.2.1 Rosuvastatin Treatment Algorithm – Statin Naïve**

**10.4.2.2 Rosuvastatin Treatment Algorithm – Statin Experienced****10.5 Removal of Study Blind**

Breaking of any blind will be available to the PI through an IWRS. The subject's treatment assignment will be available to the PI in the event of a medical emergency or an AE that necessitated identification of the study drug for the welfare of that subject. Except in the case of a medical emergency, the PI and clinic staff will remain blinded during the conduct of the study and until such time that all discrepancies in the clinical database are resolved (i.e., at the time of the database lock). The date and time when the PI removed the study blind for an individual subject will be documented by the IWRS, and an automated notification will be sent to the Sponsor.

## 11 Adverse Events

### 11.1 Definition and Grading Intensity of Adverse Events

An AE is defined as any untoward medical occurrence in a subject of clinical investigational participation administered a pharmaceutical product, whether or not considered drug related. A TEAE is an AE that is reported after a dose of study drug.

AEs include the following:

- Unfavorable changes in general condition
- Subjective or objective signs/symptoms
- Concomitant diseases or accidents
- Clinically relevant adverse changes in laboratory parameters observed in a subject in the course of a clinical study

AEs comprise all disturbances of general health status, subjective and objective disease symptoms (including laboratory abnormalities), and accidents observed in the context of a clinical trial, irrespective of a possible causal relationship with the administration of the trial substance. Events occurring in the framework of a clinical trial during drug-free and post-treatment periods or under placebo are also to be designated as AEs.

All AEs regardless of how identified (e.g., volunteered, elicited, noted on physical examination) will be recorded throughout the study from the time the patient signs informed consent through Follow-up.

Subjects will be followed for resolution of AEs, by querying the subjects for an ongoing AE until resolved or until any unresolved AEs are judged by the PI to have stabilized or if lost to follow-up. Resolution of all AEs will be promptly documented by the clinic on the subject's CRF.

Any pregnancy diagnosed during the study must be reported immediately to the PI and Sponsor, including pregnancy in female partners of male subjects. The pregnancy will be followed to term and/or outcome and this outcome must be reported to the Sponsor.

Pregnancy, in and of itself, is not regarded as an AE or SAE unless the birth results in a congenital anomaly/birth defect or there is suspicion that the study medication may have interfered with the effectiveness of a contraceptive medication or method.

The PI will rate the severity of AEs using the CTCAE v4.03 to grade the severity. Each CTCAE v4.03 term is a Medical Dictionary for Regulatory Activities (MedDRA) Lowest Level Term (LLT). The CTCAE displays Grades 1 through 5 with unique clinical descriptions of severity for each AE. Not all Grades are appropriate for all AEs. Therefore, some AEs are listed with fewer than five options for Grade selection. Grade 5 (Death) is not appropriate for some AEs and, therefore, is not an option.

## 11.2 Criteria for Determining Relationship to Drug

The PI will make a blinded determination of the relationship of the AE to NGM282 (including placebo) in the double-blind cohort. An open-label determination of the relationship of the AE to NGM282 and a separate open-label determination of the relationship of the AE to rosuvastatin will be made in the open-label single-blind cohort. The PI will make a blinded determination of the relationship of the AE to NGM282 (including placebo) and a separate open-label determination of the relationship of the AE to rosuvastatin in the placebo-controlled 24-week histology cohort. All determinations of relationship will be made using a four-category system (not related, possible, probable, or definite) according to the following guidelines:

- **NOT RELATED** = an AE that does not follow a reasonable temporal sequence from administration of the drug and that can be reasonably explained by other factors, including underlying disease, complications, concomitant drugs, or concurrent treatment;
- **POSSIBLE** = an AE that follows a reasonable temporal sequence from the administration of the drug (including the course after withdrawal of the drug) and that cannot be excluded as being possibly caused by the drug (e.g., existence of similar reports attributed to the drug and/or its analogues; reactions attributable to the pharmacological effect of the drug), although other factors such as underlying disease, complications, concomitant drugs, or concurrent treatment are presumable;
- **PROBABLE** = an AE that follows a reasonable temporal sequence from administration of the drug (including the course after withdrawal of the drug) and that can be excluded as being possibly caused by other factors, such as underlying disease, complications, concomitant drugs, or concurrent treatment.
- **DEFINITE** = an AE that follows a reasonable temporal sequence from administration of the drug (including the course after withdrawal of the drug), follows a known or hypothesized cause–effect relationship, and (if appropriate) satisfies the following:
  - Positive results obtained in drug sensitivity tests
  - Toxic level of the drug present in blood or other body fluids

## 11.3 Reporting

An SAE is any untoward medical occurrence at any dose that results in any of the following outcomes:

- Death
- A life-threatening event (i.e., places the subject, in the view of the PI, at immediate risk of death)
- Inpatient hospitalization or prolongation of existing hospitalization

- A persistent or significant incapacity or substantial disruption of the ability to conduct normal life functions
- A congenital anomaly/birth defect
- Important medical events that may not result in death, be life-threatening, or require hospitalization may be considered SAEs when, based upon appropriate medical judgment, they may jeopardize the subject and may require medical or surgical intervention to prevent one of the outcomes listed in this definition.

An unexpected adverse drug event is any adverse drug event the specificity or severity of which is not consistent with the current IB or, if an IB is not required or available, the specificity or severity of which is not consistent with the risk information described in the general investigational plan or elsewhere in the current application.

An AE is associated with the use of the drug if a reasonable possibility exists that the event may have been caused by the drug.

SAEs that are unexpected and related to either NGM282 or rosuvastatin are reportable to Regulatory Authorities. All SAEs will be reported by the PI to the Sponsor and will be reported to the responsible Ethics Committee (EC) in accordance with local requirements.

The Sponsor's assigned Safety Representative will be notified in writing (e.g., email or facsimile) within 24 hours of when an SAE is first recognized or reported. The Safety Representative will subsequently notify the Sponsor and the Sponsor's assigned Medical Monitor of all reported SAEs.

#### **11.4           Cardiovascular Adjudication**

An external independent Cardiovascular Adjudication Committee (CAC) will adjudicate serious adverse events (SAEs). The CAC members will be independent of the Sponsor, the clinical study sites and Investigators. The blinded medical review of known or suspected Major Adverse Cardiovascular Event (MACE) will primarily focus on CV death, myocardial infarction, cerebrovascular accident (stroke), and hospitalization for heart failure. Sites may be asked to provide additional source documentation relevant to any event reported to the CAC as they would to study safety personnel for any serious safety event. Further details are retained in the CAC Charter for the NGM282 Program.

### **12           Data Analysis and Statistical Considerations**

Data analysis will be performed according to the Sponsor's or its representatives' Standard Operating Procedures (SOPs).

Details of statistical parameters and methods to be applied will be provided in a detailed Statistical Analysis Plan (SAP) prior to database lock (unblinding). The general analytical approach for all endpoints will be descriptive in nature.

Unless otherwise stated, the following statistical approaches will be taken:

- Continuous variables: Descriptive statistics will include the number of non-missing values, mean, standard deviation (SD), median, minimum, and maximum. The minimum and maximum values will be presented to the same number of decimal places as recorded in the CRF; mean, median, and SD will be presented to one more decimal place than the raw data.
- Categorical variables: Descriptive statistics will include frequency counts and percentages per category. Percentages will be rounded to one decimal place, with the denominator being the number of subjects in the relevant population.
- Imputation: No missing data will be imputed.
- PK data: Descriptive statistics will include the coefficient of variation. Arithmetic mean and SD will be substituted with geometric mean and SD for all PK-concentration descriptive statistics.
- Confidence intervals (CIs): CIs will be two-sided and will use 95% confidence levels. Any analyses requiring significance testing will use a two-sided test at the 5% significance level.
- Baseline: Baseline will be defined for each patient and will be defined as the last available, valid, non-missing assessment prior to start of first study-drug administration. Unknown, Not Done, Not Applicable, and other classifications of missing data will not be considered when calculating Baseline observations. However, valid categorical observations will be considered for Baseline calculations.
- Analyses: Parametric tests will be used where all statistical requirements are met (e.g., normal distribution). In the event that statistical requirements are not met, non-parametric alternatives will be utilized.

## 12.1 Sample Size

For the double-blind cohort, a sample size of 75 subjects was selected (25 subjects per treatment arm).

Allowing for a dropout rate of 10% the following sample-size sensitivity calculations were based on a minimum number of 22 subjects per treatment group completing the trial.

A 5% difference in total liver fat content is the minimal appreciable difference that would be considered clinically relevant between the active treatment arms and the placebo treatment group. If the NGM282 3-mg and 6-mg groups are assumed to have at least a 6% reduction in liver fat when compared to Baseline along with a reduction of 1% or less from Baseline in the placebo group, with a 5% level of significance, the following illustrates sample-size

power calculations based on varying common standard deviations to achieve an overall (overall F-test) statistically significant treatment effect:

Method	Mean Absolute Change from Baseline			Common SD	Effect Size	Power
	NGM282 6 mg	NGM282 3 mg	Placebo			
One-way analysis of variance (equal n's)	6%	6%	1%	8%	0.0868	54%
	6%	6%	1%	7%	0.1134	66%
	6%	6%	1%	6%	0.1543	80%
	6%	6%	1%	5%	0.2222	92%

SD = standard deviation.

A maximum sample size of 100 subjects was selected (with a minimum of 15 subjects per treatment arm, up to a maximum of 25 subjects per treatment arm) for the single-blind cohort design.

The sample size for the open-label single-blind cohort was not based on a formal sample-size calculation. Instead, it was based on the results of the interim analysis that was conducted when ~15 subjects per arm had completed 12 weeks of treatment. Although the results of this interim analysis are still blinded, the magnitude of the treatment differences observed indicate that a sample size of 15–20 subjects per treatment arm is sufficient to give an initial indication of efficacy for further exploration.

The sample size of the placebo-controlled 24-week histology cohort is based on 1) 12-week histologic response data from the 3-mg cohort and 2) estimated placebo histologic response rates from controlled Phase 2 studies in NASH. Preliminary 12-week histologic response data (n=16) demonstrated that 50% of subjects had a 1-stage improvement in fibrosis with no worsening of NASH or resolution of NASH with no worsening of fibrosis. The placebo histologic response rates from recent Phase 2b trials of obeticholic acid, cenicriviroc, liraglutide, and selonsertib were 14%–20% at timepoints ranging from 24 to 72 weeks. Based on these data, the assumptions of calculated sample-size estimates for 24-week efficacy used an NGM282 response of 50% versus 15% for placebo utilizing 80% power and alpha=0.05 with a 2:1 randomization scheme. Assuming a 15% drop-out rate, the planned sample size of 50 NGM282-treated subjects and 25 placebo subjects is sufficient to evaluate efficacy and support powering estimates for a late-stage clinical trial.

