### **12.3 Test of Hypothesis and Significance Levels**

The null hypothesis being tested for this study will be that there is no difference in the absolute change in liver fat content from Baseline between the NGM282 and the Placebo treatment groups at EOT for the double-blind cohort. The alternative hypothesis being tested will be that there is at least a 5% difference in the absolute change in liver fat content from Baseline between the NGM282 and the Placebo treatment arms at Week 12 for the double-blind cohort. A two-sided analysis will be conducted at a 5% significance level.

Comparisons across the cohorts will be exploratory and further outlined in the SAP.

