## 12.9.2 Analysis of Primary Endpoint

The analysis of the primary endpoint will be based on the Efficacy population.

The absolute change in liver fat content from Baseline to EOT will be compared between treatment groups using an analysis of covariance (ANCOVA) model with treatment group and diabetic status (double-blind cohort only) as cofactors and Baseline endpoint as a covariate. Least square means with standard errors (SEs), differences in least square means with SE, 95% CIs for the difference in least square means, and corresponding p-values will be presented. Further covariates/cofactors may be included in the modeling depending on the relevance to the endpoint analyzed and will be further described in the SAP.

In cases where the parameters do not follow a normal distribution, a non-parametric approach will be followed to analyze the difference between treatment groups.

The primary analysis for the primary endpoint will be repeated for the Per Protocol population.

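### The double-blind cohort is powered on an overall three-group F-test, but the primary analysis does not make that test decisive; if either dose can win at 5%, the stated error level and power do not describe the claim

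*Protocol*

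**What the plan says.** Protocol 12.1 gives power for the double-blind cohort, over a range of common SDs, for an "overall F-test) statistically significant treatment effect", at a 5% level and with at least 22 completers in each of three arms. It assumes that the "NGM282 3-mg and 6-mg groups are assumed to have at least a 6% reduction in liver fat", together with "a reduction of 1% or less from Baseline in the placebo group". The printed powers are 54%, 66%, 80% and 92% for SDs of 8, 7, 6 and 5. The synopsis repeats the table.

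Protocol 12.3 states a single null hypothesis for NGM282 against placebo, without saying how the two doses enter it, and adds: "A two-sided analysis will be conducted at a 5% significance level". The general rules in Section 12 say: "Any analyses requiring significance testing will use a two-sided test at the 5% significance level".

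Protocol 12.9.2 specifies an ANCOVA with treatment group, diabetic status and the baseline value. Besides the least-squares means themselves, the outputs are "differences in least square means with SE, 95% CIs for the difference in least square means, and corresponding p-values will be presented". It names no overall test, gate, test order or multiplicity adjustment.

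The supplied SAP covers only the 24-week placebo-controlled cohort (SAP 2). For the primary endpoint it points to an earlier SAP for the double-blind phase (SAP 8.1), which is not among the documents.

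**The concern.** The test whose power is stated and the p-values that the analysis section lists are not the same thing. With two doses sharing one placebo arm, the p-values of natural interest are 3 mg against placebo and 6 mg against placebo. If a reader takes either one at 5% as showing that NGM282 works, there are two chances of a false positive and nothing in the protocol allows for them. The power table would also describe a different event from the one that decides the conclusion.

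This matters because the cohort is read dose by dose. Protocol 5.4 relies on its results at 3 mg and 6 mg when explaining the doses chosen for the later cohort, and 12.3 attaches the study's only formal hypothesis to it.

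**Working it through.** **Inputs.** From Protocol 12.1: 22 completers per arm (66 in total), mean reductions of 6, 6 and 1 points, common SD of 8, 7, 6 or 5, alpha 0.05. From 12.2: three arms, 1:1:1. The residual degrees of freedom are 66 − 3 = 63. Covariates are ignored, as they are in the protocol's own calculation.

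**1. Reproduce the printed table.** The grand mean is (6 + 6 + 1)/3 = 4.333. The variance of the means is (1.667² + 1.667² + 3.333²)/3 = 5.556. The effect size is 5.556/SD², the noncentrality is 66 × effect size, and power is the probability that a noncentral F(2, 63) exceeds its central 95% point.

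| SD | Effect size | Noncentrality | Overall F-test power | Printed |
|---|---|---|---|---|
| 8 | 0.0868 | 5.73 | 54.2% | 54% |
| 7 | 0.1134 | 7.48 | 66.4% | 66% |
| 6 | 0.1543 | 10.19 | 80.3% | 80% |
| 5 | 0.2222 | 14.67 | 92.8% | 92% |

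The effect sizes match exactly and the powers to within one point. The table is correct for the overall F-test.

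**2. Power of one dose against placebo.** The noncentrality is 5/(SD × √(2/22)). At SD 6 this is 5/(6 × 0.3015) = 2.76. With a two-sided 5% t-test on 63 df, power is 53.2%, 64.5%, 77.7% and 90.4% for SD 8, 7, 6 and 5.

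**3. Error if either dose can win.** The two contrasts share the placebo arm, so with equal arms their correlation is 0.5. With both doses inactive, the chance that at least one has two-sided p<0.05 is 9.07% from the bivariate normal and 9.03% by simulation with t on 63 df (2 million trials). Independence would give 1 − 0.95² = 9.75%, which overstates it. Counting only results that favour NGM282, the chance is 4.5%, against 2.5% for a single comparison.

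**4. The same rule with the overall test as a gate.** A dose contrast counts only if its p-value is below 0.05 and the overall F-test is also significant at 5%. These figures are simulated at 22 per arm; the power and one-dose-active rows use SD 6.

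| Quantity | No gate | Gate |
|---|---|---|
| At least one false positive, both doses inactive | 9.0% | 4.2% |
| False positive for the inactive dose, other dose active | – | 4.9% |
| Power, at least one dose | 89.6% | 80.3% |
| Power, one given dose | 77.7% | 72.6% |

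With the gate, any-dose power equals the printed 80%.

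**5. An alternative for comparison.** Dunnett's adjustment (critical t about 2.264, about 0.027 per comparison) also holds 5%. At SD 6 it gives about 69% power per dose and 83% for at least one dose, so the printed table would have to be restated.

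**The case against.** The strongest reply is that the overall test may already be intended. The Statistical Methods part of the synopsis attaches the 5% level to an ANCOVA comparison between treatment groups, and the standard test of a three-level treatment factor is the overall F-test. Section 12.3 states one null, not one per dose. On that reading the contrasts are supporting output. This stands as far as it goes: a reader might infer that the powered test is never run, and the documents do not show that. They show only that no section makes it primary or a gate.

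Second, the rule that either dose suffices is inferred. Section 12.9.2 names no doses and no contrasts, and the double-blind SAP may settle the matter. The 9.0% is therefore conditional.

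Third, a reader might take 9.0% as the chance of falsely claiming benefit. It is not: it includes trials in which a dose is significantly worse than placebo. The favourable-direction figure is 4.5%, which still exceeds 2.5%.

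Fourth, the power gap is small. The printed 80% is about 2 points above single-dose power and well below any-dose power, so the mismatch does not show that the cohort is too small.

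Finally, this is phase 2, and Section 12 calls the general approach descriptive. That lowers the weight of the point. It does not remove it, because 12.1 and 12.3 set out a formal hypothesis, a level and a power.

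**Conclusion.** The mismatch is real, and moderate in size. The powered test and the listed primary outputs differ, and the protocol does not connect them. If success means two-sided p<0.05 for either dose with no gate, family-wise error with both doses inactive is about 9.0% (4.5% in the favourable direction, against 2.5%), and the printed 80% at SD 6 describes neither single-dose power (77.7%) nor any-dose power (89.6%).

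This rests on three assumptions: that success rule, which the protocol does not state; no overriding rule in the double-blind SAP; and the protocol's own planning inputs of 22 per arm and a common SD, without covariate adjustment.

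**What to change.** Check the double-blind SAP first. If it does not already settle the order of testing, state in 12.9.2 that the overall ANCOVA treatment test at 5% is the primary test for this cohort, and that the dose-placebo p-values are interpreted as significant only if it is significant. With three groups this keeps family-wise error at or below 5% and makes the power table describe the procedure.

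The cost is one sentence, a p-value that the fitted model already yields, and about 5 points of power for a single dose (77.7% to 72.6% at SD 6). No further patients are needed.

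Treatment-group results are already known: Protocol 5.4 cites the cohort's results by dose, and 5.7 describes an analysis of 43 subjects who completed 12 weeks. A gate added now cannot be called prespecified. The report should give the overall p-value beside the dose contrasts and say when the rule was adopted.
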